### 3.8 Randomization and Intervention Delivery

After enrollment, participants will be randomly assigned to one of the two intervention arms as described in Section 2.4. Interventions will be delivered as described in Section 6.

### 3.9 Follow-up Assessment Procedures

*Cross-reference: UNC IRBIS Application section A.4.4, A.4.6, B.3.2 (number of contacts), C.1.1 (data sources)*

We will use a comprehensive, multimode data collection method that includes the collection of patient-reported outcomes through web-based and telephone approaches and leverage existing harmonized EHR data maintained by the PCORnet STAR CRN.

We will collect follow-up data in two ways:

1. EHR data extraction from the PCORI Patient-Centered Clinical Research Network (PCORNet) STAR CRN.
2. Patient surveys to collect patient-reported outcomes data.

### 3.9.1 Clinical Data Extraction

We will extract existing clinical data to measure the primary outcome of opioid dosage at baseline, 6, 12, and 18 months. Clinical data will be extracted from the PCORnet STAR CRN data warehouse, which will add efficiency and consistency to the project while reducing delays related to data access and management. Data extraction and transfer procedures are described in section 10.2.1 below.

### 3.9.2 Self-report Survey

Follow-up assessments will include the collection of patient-reported outcomes data via self-report surveys at two follow-up timepoints: 6 and 12 months after enrollment. The **T2 and T3 Follow-Up Survey** is included in the Appendix. The measures included in the surveys are described in Section 4.

Each clinical site will provide participant contact information for randomized study participants to RTI so that research staff at RTI can conduct follow-up recruitment at T2 and T3. Clinical site staff may assist in contacting hard-to-reach participants.

Access to technology and individual preferences for completing the surveys will differ across participants. To increase retention and data quality, the survey can be self-administered via the Web or on paper or administered verbally by study staff.

Staff will collect survey data according to a Follow-Up Protocol in the study Manual of Procedures. Our data collection approach is based on standard best practices in the field of survey research. Our phone follow-up protocol is consistent with best practices including that used by the CDC Behavioral Risk Factor Surveillance System (BRFSS).

#### *Introduction/Lead letter or email*

One week prior to follow-up survey data collection at T2 and T3, RTI study staff will send a lead letter/email to enrolled participants. The purpose of the lead letter/email is to remind the participants about the follow-up surveys. The lead letter/email can be found in the Appendix (**T2 and T3 Recruitment Materials document**)

#### *Web-based Administration*

RTI study staff will send participants up to 4 emails over 4 weeks with a private, secure survey link, asking them to complete the survey. Email reminders can be found in the Appendix (**T2 and T3 Recruitment Materials document.**)

We will ask enrolled participants to complete the survey by phone or by mail if they a) do not complete the follow-up Web-based survey within 4 weeks or b) do not have a valid email address.

If a participant does not complete the web survey after 4 weeks, we will close the web survey option.

#### *Computer-Assisted Telephone Interviewing Administration*

RTI study staff will contact participants who a) do not complete the follow-up Web-based survey approximately 4 weeks after the initial invitation or b) do not have a valid email address.

For participants who do not have a valid email address, we will make up to 9 contacts over a 6-week period. For participants who have a valid email address but did not complete the web survey, we will make up to 5 phone contacts over a 2-week period. A contact is defined as when the caller reaches

someone live, by voicemail, or by text message. The calls will be made at varying days and times to increase the chance of reaching the participant.

We will ask the participant to complete the survey via telephone using standard telephone interviewing techniques for Computer-Assisted Telephone Interviewing (CATI). Phone scripts can be found in the Appendix (**T2 and T3 Recruitment Materials document**).

#### *Mail Administration*

Study staff may mail participants a paper copy of the T2/T3 survey for the participant to fill out and mail back at no cost to the participant.

#### *Hard-To-Reach Protocol*

Before a participant is deemed lost to follow-up, study staff will make every effort to regain contact with the participant.

RTI staff will use web-based location resources—such as search engines, Superpages.com, etc.—and will check with local site study staff to update contact information.

RTI will notify the local site study staff of participants who cannot be reached. The research coordinator may follow-up with the participant to remind them about the survey and to set up an appointment time for RTI to call the patient to conduct the survey.

#### *Strategies for Retention*

Because the study involves enrollment over several months, we will use procedures to enhance participant retention, including the following:

- Using multiple methods for contacting participants.
- Using study reminders.
- Providing incentives for survey completion and clinic visit attendance (described below).
- Confirming current personal contact information with the participant.
- Giving patients an **INSPIRE Appointment and Survey Reminders Handout** (see Appendix) that summarizes their steps for taking part in their assigned intervention in one clear, easy-to-read page.
- Sending a periodic newsletter to enrolled participants. The newsletters will include information such as survey and intervention reminders, background on what the study hopes to achieve, and stories from SAC members. Any pictures used will be stock images (no patients or study participants will be pictured). Newsletter content will be submitted to IRB for approval.

Additionally, institution leadership will meet regularly and obtain input from the SAC, which includes patient members, to review and assess retention.

#### **3.9.3 Qualitative Data Collection**

We will also qualitatively assess the patient-reported experience as part of this pragmatic trial by conducting virtual individual interviews with participants in Arm 1 and virtual focus groups with those in Arm 2.

#### *Number of participants*

Total anticipated recruitment in the qualitative research is up to 78 participants. For Arm 1, we will recruit up to 24 participants for individual interviews. For Arm 2, we will conduct up to six focus group sessions. We will recruit up to 9 participants for each focus group, for a total of 54 participants.

#### *Recruitment*

We will ask participants during the consent process for the main study for permission to contact them for additional research activities related to this study. RCs will contact the participants who gave permission to be re-contacted using a standard script (**See Attachments, Qualitative Recruitment Materials**). During recruitment, the RC will confirm that the participant is willing and able to take part in a web conference call and will ask the participant upfront if they agree to be audio-recorded if they decide to participate.

#### *Informed Consent*

The RC will send the participant a confirmation email with a copy of the informed consent form (**see attachments, Informed Consent for CBT Participant Focus Group and Informed Consent for SDM Participant Interview**).

At the beginning of the qualitative session, the interviewer will review key points of the informed consent with the participant(s) and ask if they have any questions. The moderator will ask each participant to provide verbal consent to participate and the notetaker will document the consent.

#### *Interview and Focus Group Administration*

An interviewer and note-taker, both from RTI, will facilitate the interviews and focus groups. The moderator will use a semi-structured moderator guide (**see attachments, CBT Focus Group Guide and SDM Interview Guide**) to gather data on participant experiences with the interventions, communication with their health care providers, pain management, and opioid use. We will conduct the interviews and focus groups via a web conferencing platform. Each session will last up to 60 minutes. To facilitate engagement, we will ask participants to turn on their video/webcam if able. For privacy and security reasons, we will not video record the session. We will only record audio from the session. We will use the audio recordings to create transcripts, both of which will be stored on a password protected portion of the project share drive. The RC will mail participants a \$75 gift card at the conclusion of the focus group or interview as a thank you for their participation.

### **3.10 Incentives for Study Participation**

*Cross-reference: UNC IRBIS Application section A.9.3 (SSNs), B.4.1 (incentives), B.4.2 (incentives)*

The following incentive will be provided for study participation:

- Participants will receive a \$30 incentive payment for completing the baseline survey.
- Participants will receive a \$25 incentive payment for each follow-up survey completed.
- Participants will receive a \$10 incentive payment for each group CBT-CP session completed.

If the participant completes the T1 survey remotely or completes a group CBT-CP session remotely, the RC will mail them the incentive and **Thank You Letter with Incentive** (see Appendix). The incentive

payments for the follow-up surveys will include the **T2/T3 Thank You Letter**, which is included in the Appendix.

The total compensation a subject could receive for either arm is under \$200, therefore we are not collecting SSNs for payment. Participants receiving an incentive payment in person will be asked to sign a receipt form acknowledging receipt.

If they choose to take part in the additional qualitative research activities, participants will receive a \$75 incentive payment for completing a qualitative interview or focus group.

### 3.11 Study Completion

The patient's participation in the intervention is complete about 12 months after the completion of the T1 baseline survey; participation in the study is complete after completion of the T3 survey.

Key tracking data pertaining to visit completion and follow-up completion will be captured. These tracking data will be used to coordinate the distribution of incentive payments to participants and to identify trends in data collection; for example, to identify patterns of loss to follow-up that can inform outreach methods.

### 3.12 Withdrawal from the Study

*Cross-reference: UNC IRBIS Application section A.7.3.*

Participants are free to withdraw from participation in the study at any time upon request. An investigator may discontinue or withdraw a participant from the study for the following reasons:

- If any adverse event (AE) or other medical condition or situation occurs such that continued participation in the study would not be in the best interest of the participant.
- Disease progression that requires discontinuation of the study intervention.
- If the participant meets an exclusion criterion (either newly developed or not previously recognized) that precludes further study participation.

The reason for participant discontinuation or withdrawal from the study will be recorded in the Enrolled Participant Database. The study will retain participant data collected prior to withdrawal. We will not contact the participant to obtain any more self-report data, and the participant will not receive any further intervention. However, if the participant has completed any part of the intervention, we would like to continue to extract the participant's EHR data, and we will use the **Withdrawal Consent Addendum** (see Appendix) to seek permission to do so. If the participant withdraws prior to participating in the intervention, we will not collect any more of their data.

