The primary analyses will be based on the intention-to-treat (ITT) principle, with data from all participants analyzed according to the arm to which they were randomized irrespective of intervention received, as will key secondary analyses of pain interference and function. As in most clinical trials, some participants in this trial may not adhere to the intervention they were allocated to receive or comply with the intervention as prescribed, reducing fidelity to the intervention as designed and potentially changing the effectiveness of the intervention. The most likely form of noncompliance will be absence from group therapy sessions in the MI+CBT-CP arm or with patients on the SDM arm ceasing interaction with the assigned provider. The potential impact of this noncompliance is the dilution of the true treatment effect. In addition to the ITT analyses described above, we will conduct secondary analyses using a per protocol population that received a substantial portion of the randomized intervention, defined as at least 4 SDM sessions and at least 4 MI or CBT sessions. Details of the definition of this per protocol population will be provided in the Statistical Analysis Plan. The analysis plan will be drafted prior to the receipt of the initial PCORnet data extraction (Section 2.6) and finalized prior to REDCap study database lock and the final PCORnet data extraction.

Secondary analyses also will explore differences in the intervention effect according to participant characteristics, such as age, health literacy level, patient-centered communication, baseline pain level, baseline opioid dose, body mass index, and the presence of physical comorbidities, mental health comorbidities, or a history of substance abuse.

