#### *Distribution of Patient Materials for Arm 1*

SDM patient materials will only be provided to participants who have been randomized to Arm 1 of the study. The Research Coordinator will provide the **SDM Combined Patient Packet** (see Appendix) to the participant at the enrollment visit, electronically, or by mail. The SDM Patient Packet will include all the educational handouts (e.g., decision aids) so that participants who do not have Web access will have these documents. The packet will also contain links to Web-based versions of the materials for those who prefer to view the materials electronically. Participants will be strongly encouraged to review the suggested materials before each visit with the SDM provider.

To provide some structure to the SDM intervention, we have asked clinicians to review one or more study aids at each SDM visit as appropriate. The structure is intended to have some flexibility based on needs of the individual patient while providing guidance about content and order.

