## 6.3 MI+CBT-CP Intervention

Participants in Arm 2 will receive guideline-concordant pharmacotherapy, plus an empirically-based behavioral pain management behavioral therapy intervention, including MI to enhance motivation for active participation in CBT-CP and for opioid dose reduction or cessation, and CBT-CP for pain-coping skills enhancement. The MI+CBT-CP intervention is an empirically based behavioral pain management therapy intervention. MI and CBT-CP have both been used effectively with chronic pain.

### 6.3.1 Enrollment Procedures for Arm 2

For Arm 2 participants, the GCC portion of the intervention will be delivered by the participant's primary care provider or pain specialist who is participating in the study and has been trained. The participant will continue to see the same provider for opioid management regardless of whether their provider is trained in SDM or not. Because Arm 2 participants will not receive SDM decision aids, the providers will be trained not to use SDM with these patients (even if they have been trained in SDM).

Licensed clinicians, including masters- or PhD-level psychologists, licensed clinical social workers, or licensed professional counselors, will deliver the MI+CBT-CP intervention. To verify the training of MI+CBT-CP providers, RTI will request proof/documentation of fulfilling the study's MI+CBT-CP training from each MI+CBT-CP provider. However, the MI/CBT-CP providers are clinical staff at their respective institutions and have experience with MI and CBT-CP. Thus, training will focus on the study MI/CBT-CP protocol, and not MI or CBT per se.

The intervention will include 1 individual MI session as soon as this session can be scheduled after enrollment and up to 8 CBT-CP group therapy sessions. We anticipate the MI+CBT-CP component of the intervention may occur within 3 months of enrollment but could extend longer. The process for scheduling the participant may vary slightly based on the institution or clinic. Study or clinic staff will continue to follow up with the participant until the individual MI visit and the group CBT sessions are scheduled. The goal will be to arrange for CBT to begin as soon as possible after the baseline interview.

The participant will be asked to attend one individual MI session that will last about 30 to 60 minutes, either in-person or via the clinic's telehealth platform.

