4.6 Database Lock

As noted above, 3 different study databases will provide data. The last participant is expected to be enrolled in March 2022 and the last intervention visit may go until March 2023. The last T2 (6-month) survey is expected in September 2022 and the last T3 (12-month survey) is expected in March 2023. The T2 and T3 survey database will be locked approximately one month after the last completion of the T3 survey. The REDCap database lock will occur after the last participant's final intervention status CRF has been completed (i.e., completed the 12-month intervention phase) and all data queries have been resolved by the study sites. As mentioned above in section 4.4.3, the EHR data extraction takes places 3 times across the study. *Although the final EHR data extraction is planned to take place in July or August 2023, or 18-months after the last participant was enrolled into the study, it will likely not contain 18-months of EHR data for the last participant since there is up to a 3-month lag between clinic visit and data inclusion in the CDM. However, all participants should contain 12-months of EHR data in the final extraction (the study's primary timepoint).* The final EHR data extraction will be considered final and locked after the sites have addressed any potential RTI queries and transferred a clean dataset (expected to occur ~2-months after the initial data transfer). The locked datasets from each of the 3 databases will be used to derive the final analysis dataset which will be used to perform the analyses described within this SAP. Analysis data specifications are further described in section 9.2.

The study is designed as intention-to-treat (ITT). If a participant discontinues further intervention or participation in the study, every attempt will be made to continue to perform the required study-related follow-up surveys and EHR data extraction. However, surveys and EHR data will not continue to be collected from those who are determined ineligible, withdrew from all study activities, investigator withdrew and other (depending on the reason).

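### Protocol 3.12 makes EHR dose after withdrawal observable only for participants who had started the intervention; the same opt-in permission should be sought from every randomised participant who withdraws

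*Protocol*

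**What the plan says.** Protocol 3.12 separates withdrawers by whether they had begun the intervention.

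- Begun: "if the participant has completed any part of the intervention, we would like to continue to extract the participant's EHR data", with permission sought through the Withdrawal Consent Addendum.
- Not begun: "If the participant withdraws prior to participating in the intervention, we will not collect any more of their data". No addendum is mentioned.
- Both: "The study will retain participant data collected prior to withdrawal".

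Protocol 5.1 bases the primary analysis on intention to treat, "with data from all participants analyzed according to the arm to which they were randomized irrespective of intervention received". SAP 5.1 repeats the principle and uses participants wherever their data are available.

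SAP 4.6 handles the same situation differently. When a participant discontinues, "every attempt will be made to continue to perform the required study-related follow-up surveys and EHR data extraction". Its next sentence stops surveys and EHR collection for those found ineligible, those who leave all study activities, those withdrawn by the investigator, and some others depending on the reason. It mentions neither receipt of intervention nor the addendum.

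The arms start by different routes. Arm 1 participants receive the SDM packet "to the participant at the enrollment visit, electronically, or by mail" and meet an SDM-trained provider at opioid management visits, in some cases after changing provider (Protocol 6.2.1). Arm 2 participants have "1 individual MI session as soon as this session can be scheduled after enrollment", followed by group CBT, and "Study or clinic staff will continue to follow up with the participant until the individual MI visit and the group CBT sessions are scheduled" (Protocol 6.3.1).

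**The concern.** The outcome is prescribing recorded in the EHR, so a participant need not receive any intervention for it to be measured. A rule that ends measurement only for those who have not begun creates avoidable missing data, and ties it to something that happens after randomisation and after the participant knows the assignment.

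The people affected are those who leave on learning their arm or while waiting to start. Reasons for leaving at that stage can be specific to an arm: a change of prescriber in Arm 1, or waiting for sessions and possible co-pays in Arm 2. If those who leave would have changed their dose differently from those who stay, and the lost shares differ, the comparison at 12 months is biased.

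The planned model gives limited protection. Its response is change from baseline at months 3 to 18 (SAP 9.3), so a participant with no usable post-baseline interval contributes nothing. For these people the missing-at-random assumption rests on arm, site and baseline dose alone, because there are no earlier follow-up values to draw on.

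**Working it through.** **1. The plan's own figures.** Inputs from Protocol 5.4 and SAP 6: difference 10 MED, adjusted SD 40 MED, two-sided alpha 0.05, power 80%, inflation 20%.

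- The t-based two-sample formula gives 252.1, so 253 per arm, as stated.
- 253 × 1.2 = 303.6, so 304 per arm and 608 in total, as stated.
- With 526 randomised, 526/1.2 evaluable gives 74.4% power; SAP Table 6.1 states 75%.

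The sample size is not in error here. Protocol 5.3.3 allows for up to 12% missing dose data at 12 months and includes withdrawal of EHR consent in that figure. The allowance covers precision; it does nothing about differential loss.

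**2. How many people could be involved.** SAP 6 reports 20% study discontinuation: 0.20 × 526 ≈ 105. The documents do not split this by arm or by receipt of intervention. If 25% to 50% of these left before starting (an assumption), that is 26 to 53 people, or 5% to 10% of those randomised.

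**3. Power if such losses came on top of the planned 12%.** Evaluable per arm = 263 × (1 − 0.12 − w)/1.07, where 1.07 = 1 + 7 × 0.01 is the design effect, applied here to both arms.

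| Extra loss w | 0% | 2% | 5% | 10% |
|---|---|---|---|---|
| Power, N = 526 | 73.9% | 72.9% | 71.4% | 68.7% |

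**4. Bias.** In one arm, let a share p be lost, with mean change m_L in the lost and m_R in the retained. The observed mean exceeds the true mean by p × (m_R − m_L). If the gap is the same in both arms, the bias in the arm difference is (difference in lost share) × (gap).

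Example, all values assumed: retained −10 MED, lost 0 MED, 15% lost in Arm 2 and 5% in Arm 1.

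- Arm 2: true mean 0.85 × (−10) = −8.5, observed −10.
- Arm 1: true mean 0.95 × (−10) = −9.5, observed −10.
- Arm 2 minus Arm 1: true +1.0, observed 0. The bias is 1.0 MED in favour of Arm 2. Exchanging the two loss rates reverses the sign.

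This example implies 0.15 × 263 + 0.05 × 263 ≈ 53 people, the top of the range in step 2. Over a wider range of assumptions:

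| Difference in lost share | Gap 10 MED | Gap 20 MED | Gap 40 MED |
|---|---|---|---|
| 2 points | 0.2 | 0.4 | 0.8 |
| 5 points | 0.5 | 1.0 | 2.0 |
| 10 points | 1.0 | 2.0 | 4.0 |

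The formula uses raw means. The model adjusts for baseline dose and site, so only the part of the gap that these do not explain would remain.

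**5. Scale.** With 526/1.2/2 ≈ 219 per arm, SE = 40 × √(2/219) ≈ 3.8 MED. A 1.0 MED bias is about 0.26 SE and would raise a nominal 5% two-sided error rate to about 5.8%.

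**6. Whether the plan would detect it.** In SAP 9.4 the comparison of baseline characteristics by missingness runs only if more than 20% of 12-month MED is missing. The tipping-point analysis also needs a significant primary result. Differential loss below 20% meets neither condition.

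**The case against.** The case against is substantial, and most of it stands as a limit on the point.

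- **Nobody is removed from the ITT set.** A reader might infer that the rule excludes randomised participants. It does not: they stay in the set, earlier data are kept, and only dose after withdrawal is lost. Someone who waits some months before leaving may still contribute an interval.
- **Non-attenders are not affected.** SAP 8.1 says that participants with no intervention visits still had EHR extraction. The rule reaches only active withdrawers.
- **SAP 4.6 is not simply more generous.** It too stops collection for those who leave the study entirely. The discrepancy is that it decides by type of withdrawal, whereas Protocol 3.12 decides by receipt of intervention.
- **The timing difference is not established.** A reader might also infer that Arm 2 stays exposed to the rule for longer and so loses more people. The documents do not support a direction. Guideline-concordant care is an intervention component in both arms (Protocol Table 2, 6.1 and 6.3.1), so a routine opioid visit could count as having begun in either. Some Arm 1 participants must change provider, while Arm 2 participants keep theirs. Section 6 calls the intensity of the first three months similar. Section 8.1.3 foresees extra visits in Arm 1 as well as co-pays in Arm 2, and section 3.10 pays Arm 2 participants for CBT sessions attended. No section gives time to first contact by arm.
- **The remedy is late and needs approval.** Enrolment is closed. Opt-in extraction and the addendum came in protocol versions that answered IRB stipulations, and the form is not among the documents reviewed, so its suitability for people who never started is unknown.

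None of this defends the condition itself. That participation in the intervention is open to several readings also means that sites could apply the rule differently.

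**Conclusion.** The point holds in a limited form. Protocol 3.12 lets receipt of intervention decide whether the EHR primary outcome can be followed after withdrawal. That is at odds with an analysis meant to disregard receipt of intervention, and it does not match SAP 4.6. The trigger is undefined, assignment is unblinded, and the arms start differently, so loss related to arm is possible.

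Its direction and size are unknown. The 1.0 MED figure rests wholly on an assumed 10-point difference in lost share and an assumed 10 MED gap; the range of 0.2 to 4.0 MED is equally a product of assumptions. At 1.0 MED the effect would be small beside a standard error of about 3.8 MED. The case for change is that the loss is avoidable and may go unexamined. The documents do not show that the primary comparison is seriously biased.

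**What to change.** 1. In Protocol 3.12, remove the condition on having completed part of the intervention, and delete the final sentence.
2. Seek the same opt-in permission for continued EHR extraction from every randomised participant who withdraws, in either arm, through the Withdrawal Consent Addendum, subject to IRB approval of its wording for people who have not started.
3. Rewrite SAP 4.6 to state that single rule, so that the two documents agree on when extraction stops.
4. Report by arm the number and timing of withdrawals before any intervention, and how many withdrawers allowed EHR use. This needs a written definition of when participation in the intervention begins, applied alike at all sites.

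The cost is a minor amendment and one extra question to people who are leaving. With enrolment closed, the amendment will recover little for those who have already withdrawn. The reporting in item 4 can still be done and would let readers judge whether the loss was differential.
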